## **Methodology**

### **Participants**

NAFLD patients who attending the Gastroenterology Clinic at Hospital Universiti Sains Malaysia, a tertiary referral centre for the north-eastern Peninsular Malaysia, will be screen from August 2015 till July 2016.

During the first visit, if participants met the selection criteria, informed consent are then taken. Demographic data of participants are recorded. All participants are required to complete a two-week run-in period consisting of maintaining and self-monitoring their usual dietary and daily activities.

[figure not shown]
Participants who fulfilled the selection criteria are randomly assign to the MACR group or the control group after a 2 week run-in period. During the 2 weeks, participants are requiring to keep their body weight stable by maintaining their usual eating habits and their daily activities. Randomization is performed using a random number generator with recruitment aimed for three MACR participants for every control participant by principal investigator. Calculated sample size of 46 participants would achieve a significant difference in studied outcome between intervention and control group using a two-sided test with  $\alpha = 0.05$  and power = 0.8. Participants are blinded after assignment to interventions or control group.

### **Interventions**

#### **MACR group**

For a total of 8 weeks, participants in this group need to restrict 70% of their energy needs over 24 hours on a calorie restriction day alternate with a feeding day for the next 24 hours, where participants allowed eating whatever they wish (ad libitum). The calorie restriction and feeding days begin at 9am each day, and on the calorie restriction day, meals are consumed between 2pm and 8pm to ensure that each participant underwent the same duration of calorie restriction. The MACR protocol is shown in Figure 1. On each calorie restriction day, participants are allowed to take energy-free beverages, tea, coffee, and sugar-free gum and encouraged to drink plenty of water. Diet plans are not provided to participants but are self-selected using detailed individualized food portion lists, meal plans, and recipes. To ensure maximal adherence to dietary plan, participants received phone calls from the investigator ([name]) and 2-weekly appointments (total four appointments) with a dietician described below. Adverse experiences are assessed every 2 weeks until 1 week after the completion of trial.

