### **Control group**

All participants in the control group will continue their usual habitual diet for 8 weeks. No specific dietary advice or educations are provided throughout the entire trial.

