**Figure 2 Flow Diagram**

**Management of diabetes medications during the study period**

Previous reports found that Insulin sensitizing agents like thiazolidinediones and metformin might induce biochemical and histological effects similar with NAFLD (9-12). Therefore, participants, who were already taking thiazolidinedione or metformin, must be on a stable regimen for at least 6 months prior to this study enrolment and the regimen must remain stable during the study. All participants are not allowed to start on any of these medications during the entire study period to avoid any potential confounding effects. Participants who continue to have active disease despite on these medications should be allowed to participate in the study trial to maximize generalizability. If medically necessary, participants were allowed new medications for hyperglycaemia and the available options included sulfonylureas, meglitinides and insulin.

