## **Safety consideration**

There may be risks to you if you participate in this study. These tests are fairly safe with little risk involved. For most people, needle puncture for blood draws will cause discomfort but do not cause any serious problems. If any important new information is found during this study that may affect you wanting to continue to be part of this study, you will be told about it right away.

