### **Problems Anticipated**

Compliance to dietary modification is one of the problems anticipated while conducting the trial. To overcome this problem, 2 weekly together with designated dietician given to participants in interventional group to monitor the calorie intake as well as education regarding calorie calculations. Besides that, we also will call participants once in a week to ensure the participants comply with dietary modification.

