## **1. Subject vulnerability**

1.1 The participants who involved in the study will be provided comprehensive explanation regarding the study procedure, any known adverse reactions, anticipated benefits and potential hazards of the study. If the subject is under my care as a doctor, the patient will be given full freedom to participate or not without affecting her medical condition management and care.

1.2 Participants will not get vulnerable to the study as data obtained from this study does not identify participants individually. Besides that, the data will be independent and will not be used for any achievement assessment and decision related to work

1.3 In addition, participants are given option to terminate their involvement in the study at any time without penalty or loss of benefits if they want to stop. A list of contact number of the investigators will be included in the participants information leaflet and they can directly contact the investigator if they have any queries or opt to cease the study.

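### No adverse-experience schedule is written for the control arm and no by-arm summary is planned, so a like-for-like comparator for symptoms under MACR is not assured

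*Combined protocol and SAP*

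**What the plan says.** The combined protocol and SAP has one sentence that schedules the collection of harms: "Adverse experiences are assessed every 2 weeks until 1 week after the completion of trial". It is the last sentence of the MACR group subsection under Interventions. The sentence before it gives the MACR participants telephone calls and "2-weekly appointments (total four appointments) with a dietician described below". Problems Anticipated describes the two-weekly dietician contact as "given to participants in interventional group to monitor the calorie intake", and explains the weekly call by compliance with the diet.

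The Control group subsection has two sentences. "All participants in the control group will continue their usual habitual diet for 8 weeks", and "No specific dietary advice or educations are provided throughout the entire trial". It mentions no interim visit, call or safety enquiry.

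Procedures, which is not limited to one arm, covers weight at visits, blood tests at baseline and within a week after the intervention, and ultrasound. It attaches no question about symptoms. Data management and statistical analysis lists between-group comparisons of weight, laboratory and ultrasound variables and does not mention adverse experiences.

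Safety consideration says "These tests are fairly safe with little risk involved" and goes on to discomfort from blood sampling. It does not mention the diet. Elsewhere the document does recognise diet-related problems. Sampling Frame excludes people for whom calorie restriction is contraindicated and makes inability to tolerate the fasting a withdrawal criterion. Subject vulnerability promises participants an explanation of "any known adverse reactions, anticipated benefits and potential hazards of the study".

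**The concern.** How many symptoms a trial records depends on how often and in what way people are asked. If one arm is questioned every two weeks and the other is not questioned on any written occasion, a difference in recorded symptoms mixes the effect of the diet with the effect of asking. Complaints that are common in any clinic population would then appear as experience under MACR, with no control figure obtained in the same way to set beside them.

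The section headed Community sensitivities and benefits expects the results to support MACR as an alternative to conventional approaches. A reader weighing that claim will want tolerability by arm. As written, the plan neither assures comparable data nor says that such data would be reported.

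**Working it through.** The plan gives no figure for adverse experiences, so there is none to reproduce. The check sets the sections side by side, then sizes the gap and the gain from closing it.

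**1. Who is asked, and when**

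| Item | MACR | Control |
|---|---|---|
| Adverse-experience schedule | every 2 weeks, until 1 week after completion (MACR group) | none written (Control group) |
| Interim contact | four dietician appointments and telephone calls | none written |
| Enquiry attached to assessments in Procedures | none | none |
| Planned summary (Data management and statistical analysis) | none | none |

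Eight weeks at two-week intervals gives 8 / 2 = 4 checks (weeks 2, 4, 6 and 8). Reading the end point as a further check one week after the end gives 4 + 1 = 5. If it only closes the window, the number is 4. The written number for controls is 0.

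**2. Arm sizes**

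The Participants subsection gives a total of 46 and an aim of three MACR participants per control: 46 x 3/4 = 34.5 and 46 x 1/4 = 11.5, so about 34 against 12 (or 35 against 11).

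**3. What unequal asking could produce**

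Assume that the diet has no effect and that the same share of each arm would report some symptom if asked. The documents give no rate, so a range is shown for 34 against 12.

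| Assumed background share | MACR reports expected (34 x share) | Control reports if asked (12 x share) | Control reports if not asked |
|---|---|---|---|
| 5% | 1.7 | 0.6 | as low as 0 |
| 10% | 3.4 | 1.2 | as low as 0 |
| 20% | 6.8 | 2.4 | as low as 0 |
| 30% | 10.2 | 3.6 | as low as 0 |

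The last column is a lower limit, because controls may volunteer complaints.

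**4. What equal asking would buy**

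With no events in n people, the one-sided 95% upper limit for the true rate is 1 - 0.05^(1/n).

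- n = 12: 1 - 0.05^(1/12) = 22.1%.
- n = 11: 1 - 0.05^(1/11) = 23.8%.

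Power of a two-sided Fisher exact test at 0.05 is the sum, over all pairs of event counts with P < 0.05, of the product of the two binomial probabilities. The event rates are assumptions.

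| Assumed rates, MACR v control | 34 v 12 | 35 v 11 |
|---|---|---|
| 20% v 5% | 7% | 4% |
| 30% v 10% | 19% | 17% |
| 40% v 10% | 42% | 41% |
| 50% v 10% | 69% | 68% |

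None of these reaches the 80% that the plan sets for efficacy. Equal collection removes the difference in asking; it does not make a powered safety comparison.

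**5. Cost**

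12 controls x 5 checks = 60 calls, or 12 x 4 = 48 if there are four checks.

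**The case against.** The strongest reply is that the plan nowhere restricts safety follow-up to MACR. The sentence names no arm, although the same subsection opens by limiting its dietary rule to participants in that group. Procedures refers to weighing at visits without naming an arm, and the flow diagram (Figure 2), where a visit schedule might appear, is not available in the text reviewed. This part stands: collection in MACR alone is the likely reading, not a stated rule. It does not remove the point, because nothing tells the staff what to do for controls, and the two-weekly contacts that would carry the questions belong to the intervention group.

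A reader might also infer that the safety passages contradict each other. They do not. Safety consideration is silent on the diet; it does not say that the diet carries no risk, and it denies none of the monitoring, exclusion or withdrawal provisions. It is also worded as if addressed to a participant, and the consent pages are not available, so its silence cannot be taken as silence in everything participants are told.

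A further tempting link is the diabetes-medication section, where for new treatment "the available options included sulfonylureas, meglitinides and insulin". That permission covers participants in general and conflicts with nothing in the safety text. Tying it to a MACR hazard needs a pharmacological argument that the documents do not make, so it forms no part of this point.

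Finally, safety is not among the stated objectives, and about 12 controls can show little. Both are true. They limit the weight of the point, but they do not justify asking one arm only.

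**Conclusion.** The point holds as a gap in specification. The only schedule for adverse experiences is placed under MACR, none is written for controls, and no summary is planned for either arm. On the likely reading, this means four or five enquiries per MACR participant against none written for controls, so a comparator obtained in the same way is not assured.

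It would go too far to conclude that controls are expressly left out, or that harm from the diet would be reliably estimated once the gap is closed. With about 34 against 12 participants, no events among 12 controls still allows a true rate of about 22%, and power for an assumed 30% against 10% is 17% to 19%. The gain is a fair descriptive comparison.

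This rests on the 3:1 split of 46 being achieved and on the MACR-only reading. The symptom rates used are illustrative assumptions. The planned efficacy comparisons are not affected. The silence of Safety consideration on the diet is a secondary wording matter. The change is worth making because it is cheap and removes an avoidable source of bias.

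**What to change.** - Move the adverse-experience sentence from the MACR group subsection to Procedures. State that it applies to both arms, with the same standard questions at weeks 2, 4, 6 and 8 and one week after the end. In controls this can be done by telephone, with a script that gives no dietary advice.
- Add to Data management and statistical analysis a descriptive table by arm: number and percentage of participants with at least one adverse experience, and number of events by type. Say that the comparison is descriptive.
- Reconcile Safety consideration with Sampling Frame, the MACR group subsection and Subject vulnerability, so that the protocol's risk statement also covers the calorie restriction itself. No clinical rule is proposed.

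The cost is protocol wording and about 60 short calls. The downside is slightly more contact with controls than now written.

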**Figure 1 MACR protocol for the 8 weeks duration**

### **Assessment of dietary plan adherence**

[figure not shown]
A designated dietician ([name]) will provide education to participants regarding calorie restriction and help to monitor their dietary compliance. Adherence to intervention is assessed via a diet diary and dietary recall. The diary is collected and reviewed by the dietician every 2 weeks. If the diary indicates that the participants eat an extra calorie on a fasting day, that day is labelled as “not adherent.” If the diary revealed that the participant did not eat any extra food item, that day is labelled as “adherent.” Adherence data are assessed each week as 1) absolute adherence (number of adherent days with diet) and 2) percentage of adherence calculated by applying the following formula for adherence in percentage. The formula is shown below.

$$\frac{\text{Number of fast day's adherent}}{\text{Number of fast days in week}} \times 100$$

### **Control group**

All participants in the control group will continue their usual habitual diet for 8 weeks. No specific dietary advice or educations are provided throughout the entire trial.

**Figure 2 Flow Diagram**

**Management of diabetes medications during the study period**

Previous reports found that Insulin sensitizing agents like thiazolidinediones and metformin might induce biochemical and histological effects similar with NAFLD (9-12). Therefore, participants, who were already taking thiazolidinedione or metformin, must be on a stable regimen for at least 6 months prior to this study enrolment and the regimen must remain stable during the study. All participants are not allowed to start on any of these medications during the entire study period to avoid any potential confounding effects. Participants who continue to have active disease despite on these medications should be allowed to participate in the study trial to maximize generalizability. If medically necessary, participants were allowed new medications for hyperglycaemia and the available options included sulfonylureas, meglitinides and insulin.

## **Procedures**

A standardized calibrated balance (Secca, ZT-120, and Hamburg, Germany) will be used to measure weight of participants in light clothing at each visit. A wall-mounted stadiometer (Secca, ZT-120, Hamburg, Germany) is used to measure height (in m), and together with weight (in Kg), body mass index (BMI) is calculated. Waist circumferences are measured with the participants standing, and with the measuring tape kept horizontal and measured at a level midway between the superior aspect of the iliac crests and the lower lateral margins of the ribs.

Blood samples - 8-10 hours of fasting blood samples are collected at 8-10 am at baseline and within 1 week post intervention for biochemical analysis. High-density lipoprotein (HDL), low-density lipoprotein (LDL), triglycerides (TG), total cholesterol, fasting blood sugar and liver enzymes (alanine aminotransferase, ALT and aspartate aminotransferase, AST) are measured.

Ultra-sonographic measurements including liver steatosis and shear wave elastography (SWE) are performed with the SuperSonic Imagine's Aixplorer® Ultrasound machine (Super Sonic Image, Aix-en Provence, France). All measurements are performed by a single sonographer ([name]) where the inter-observer agreement level with another experienced sonographer ([name]) is 85%. Hepatic steatosis is graded as normal (grade 0), mild (grade 1), moderate (grade 2) and severe (grade 3) based on visual analysis of intensity of echogenicity with an appropriate gain setting based on standardised parameter (13-14). Homogenous echotexture and echogenicity equal or slightly more than the renal cortex and spleen are characteristics of a normal liver. Liver echogenicity would be higher than the renal cortex and spleen if there was hepatic steatosis.

Through the intercostal approach, SWE measurements are performed in the right liver lobe, at the supine position with the right arm in maximal abduction. The sonographer, assist by an ultrasonic time-motion image, located a liver portion of at least 6 cm thick, free of large vascular structures. Once the measurement area had been located, the sonographer presses the probe button to start an acquisition. Patients are asked to hold their breath for about five seconds, while the stiffness of the region of interest was measured and 10 measurements are made for each patient and the median average value of those measurements is recorded in kilopascals (kPa: metric). Based on median liver elastography values, previously published four categories could be determined for different fibrosis stage.

## **Safety consideration**

There may be risks to you if you participate in this study. These tests are fairly safe with little risk involved. For most people, needle puncture for blood draws will cause discomfort but do not cause any serious problems. If any important new information is found during this study that may affect you wanting to continue to be part of this study, you will be told about it right away.

## **Data management and statistical analysis**

Descriptive statistics are computed for all variables; means with standard deviations (SD) for continuous variables, median with interquartile range (IQR) for ordinal data and frequencies with percentages for categorical variables. Using Kolmogorov-Smirnov analysis, the data were normally distributed if the skewness is within the range of  $\pm 2$  time standard error (SE)

of skewness. Per-protocol (PP) and intention-to-treat (ITT) analysis are performed where comparison is made within-group (post- vs. pre-intervention for each intervention and control group) and between-group (MACR vs. control). Missing data are imputed using multiple imputation method. Independent *t*-test is used to analyse changes in weight, liver chemistry, lipid profile variables, fasting blood sugar and ultrasonographic changes of liver steatosis and fibrosis between the MACR and control group. SPSS version 22 (SPSS Inc., Chicago, United States) is used for all statistical analysis. All *P* values quoted were two-sided with  $P < 0.05$  considered as statistically significant. Sample size is 46 participants with 80% power of the study.

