**Sampling Frame**

Inclusion criteria

1. Age ranges 18 to 70 years old
2. Baselines Ultrasound show evidence of fatty liver
3. Elevated alanine aminotransferase (ALT) or aspartate aminotransferase (AST) values (ALT>41 or AST>34U/L)

Exclusion criteria

1. Medically or surgically ill patients who cannot consent
2. Complicated chronic liver disease with portal hypertension
3. Significant alcohol consumption (1 standard drink per day)
4. Contraindications to calorie restriction
5. Pregnancy
6. Engagement in an active weight loss program
7. Taking weight-loss medication, substance abuse
8. Significant psychiatric problems

Withdrawal criteria

1. Subject who unable to tolerate alternate daily fasting intervention during the trial
2. Patient own choice

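### The normality rule is mislabelled and leads nowhere, and unadjusted t-tests on change scores give up power that baseline-adjusted ANCOVA would mostly recover

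*Combined protocol and SAP*

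**What the plan says.** All of the analysis text is in Data management and statistical analysis.

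- **Normality rule.** "Using Kolmogorov-Smirnov analysis, the data were normally distributed if the skewness is within the range of" plus or minus two standard errors. The text does not say whether this is applied by arm or pooled, or to levels or changes. It names no transformation, rank test or other step for data that fail.
- **Between-group test.** An independent t-test "is used to analyse changes in weight, liver chemistry, lipid profile variables, fasting blood sugar and ultrasonographic changes of liver steatosis and fibrosis". No baseline covariate is mentioned.
- **Summaries.** Means and SDs for continuous variables, and "median with interquartile range (IQR) for ordinal data and frequencies with percentages for categorical variables". The Procedures section grades steatosis visually from 0 to 3, so it is ordinal.
- **Size.** The Participants section says "Calculated sample size of 46 participants would achieve a significant difference in studied outcome between intervention and control group", two-sided at 0.05 with power 0.8, and "recruitment aimed for three MACR participants for every control participant". The analysis section repeats "Sample size is 46 participants with 80% power of the study".
- **Entry.** Sampling Frame requires "Elevated alanine aminotransferase (ALT) or aspartate aminotransferase (AST) values", with ALT above 41 or AST above 34 U/L and no upper limit.

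**The concern.** A Kolmogorov-Smirnov test compares a whole empirical distribution with a reference distribution and does not use skewness. One analyst could run that test and another could divide skewness by its standard error, and they could reach different verdicts on the same data. Neither verdict would change anything, because the t-test is prescribed regardless.

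The analysis itself is the larger matter. Enzymes, lipids and ultrasound measures all fall under the primary objective, the control arm has only about 12 people, and baseline values are collected for everyone but used only to form a difference. A change score fixes the coefficient on baseline at 1. When the true coefficient is lower, that adds noise to the comparison. The plan also treats steatosis grade as ordinal when describing it and as continuous when testing it.

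**Working it through.** **Inputs from the documents.** Total 46, allocation 3:1 (about 34 and 12), two-sided 0.05, power 80%.

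**Assumed, because the documents are silent.** Log-scale SD 0.4-0.6, pre-post correlation on the log scale 0.5-0.7, and a true proportional fall of 25% or 30% in the MACR arm.

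**Step 1: the plan's own figure.** The 46 cannot be reproduced, since no outcome, SD or difference is given. Solving backwards at 3:1, the detectable standardised difference is (1.960 + 0.842) × √(1/11.5 + 1/34.5) = 2.802 × 0.3405 = 0.954. The exact t calculation at 34 and 12 gives 0.962. So the design has 80% power only for a difference of nearly one SD, and efficiency matters.

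**Step 2: the skewness limit.** SE = √[6n(n−1) / ((n−2)(n+1)(n+3))].

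- n = 12: √(792/1950) = 0.637, limit ±1.27
- n = 34: √(6732/41440) = 0.403, limit ±0.81
- n = 46 pooled: √(12420/101332) = 0.350, limit ±0.70

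At log-SD 0.5, log-normal levels are flagged 30% of the time at n = 12 and 75% at n = 34. The t-test is applied to changes, and these are flagged less often: 19% in controls and 51% in MACR (correlation 0.7).

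**Step 3: why adjustment helps.** With equal variances σ² and correlation ρ, a change score has variance 2σ²(1−ρ), and the ANCOVA residual variance is σ²(1−ρ²). The ratio of the second to the first is (1+ρ)/2, which is 0.75 at ρ = 0.5 and 0.85 at ρ = 0.7. Under a proportional fall the treated arm's follow-up values also shrink. Their slope on baseline then moves further from 1, and the gain is larger.

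**Step 4: simulated power at 34:12.** Log baseline is s·Z₀. Log follow-up is s·(ρZ₀ + √(1−ρ²)·Z₁), plus ln(0.70) in the MACR arm for a 30% fall or ln(0.75) for a 25% fall.

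| Setting | Raw-change t-test (plan) | Log-change t-test | Raw ANCOVA | Log ANCOVA |
|---|---|---|---|---|
| log-SD 0.5, ρ 0.7, 30% fall | 61% | 78% | 78% | 83% |
| log-SD 0.5, ρ 0.7, 25% fall | 44% | 57% | 59% | 64% |
| log-SD 0.4-0.6, ρ 0.5-0.7, 30% fall | 31-82% | not tabulated | 48-94% | 51-95% |
| Additive effect, normal data, CV 0.3 | 71% | not tabulated | 77% | 65% |

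Type I error is near 5% for every method under the log-normal model.

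**Step 5: splitting the gain.** In the first row, raw ANCOVA recovers 78 − 61 = 17 of the 83 − 61 = 22 points that log ANCOVA recovers. At the low end of the range it recovers 48 − 31 = 17 of 51 − 31 = 20, and at the high end 94 − 82 = 12 of 95 − 82 = 13. The log-change t-test also reaches 78% in the first row, so the two routes overlap and their gains do not add.

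**Step 6: the additive case.** In the last row raw ANCOVA gains 77 − 71 = 6 points; with other settings the gain is about 6-12. Log ANCOVA falls 77 − 65 = 12 points below raw ANCOVA and below the planned test. In a separate model with a log-normal baseline and normal changes, the raw-change t-test keeps 79-80% and the log-change t-test has 61-64%.

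**The case against.** The strongest reply is that nothing here threatens validity. Type I error stays near 5%, the check does no harm if it has no consequence, and the power loss rests on distributions that the documents do not supply. With mild skew, or with effects that are additive and unrelated to baseline, the planned test loses little. The reply stands on validity and on the conditional nature of the figures. It does not rescue the rule, which is mislabelled and leads nowhere whatever the data look like.

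A reader might infer four stronger points that the documents do not support:

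- **That skewed enzymes and triglycerides make the raw-scale test substantially weaker because of skewness.** No distribution is given, changes are less skewed than levels, and most of the shortfall is recovered without taking logs.
- **That the rule is laxest in the control arm.** This holds only if it is applied by arm, which is not stated. Pooled, there is a single limit of ±0.70.
- **That entry truncates both enzymes from below.** The criterion is either/or, so neither enzyme is truncated individually, and triglycerides have no entry limit. Right skew is plausible but not established.
- **That the method will be chosen after the data are seen.** The text leaves room for this, but it does not say so.

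**Conclusion.** The wording defects are certain and need no assumption: the named test is not the rule, the rule has no consequence, and an ordinal grade is assigned a t-test. The power loss is conditional. Under log-normal markers with a 30% proportional fall, raw-scale ANCOVA gains about 12-17 points over the planned test at the settings compared, and the log scale adds about 1-5 more. With additive effects and normal data, raw ANCOVA gains about 6-12 points. That gain shrinks towards nothing as the slope of follow-up on baseline approaches 1. The case for adjusting for baseline therefore holds under both types of effect, whereas the case for logs depends on proportional effects. This is worth changing before analysis, but it is a loss of efficiency and clarity and does not make the results invalid.

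**What to change.** - Delete the normality rule and the reference to Kolmogorov-Smirnov.
- For every continuous outcome, in both the intention-to-treat and per-protocol analyses, replace the change-score t-test with ANCOVA of the follow-up value on group and baseline. Report the adjusted difference with its 95% confidence interval.
- State the scale for each outcome in advance. Use logs only where right skew and proportional effects are expected (ALT, AST and triglycerides are candidates), report those results as ratios, and acknowledge that power can be lost if the effect proves additive. Keep the raw scale elsewhere.
- Analyse the 0-3 steatosis grade with an ordinal or rank method, in line with how the plan already summarises ordinal data.

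The cost is a revision of the analysis text. Baselines are already collected, the methods are available in SPSS 22, and no extra participants or visits are needed. The one trade-off is that log-scale results are read as percentage changes.

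### The per-protocol set is undefined and ranks equally with ITT; the plan's only diet-adherence and intolerance criteria can apply to MACR alone, so a comparison built on them would be selected in one arm on diet and not in the other.

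*Combined protocol and SAP*

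**What the plan says.** Under Data management and statistical analysis, the plan states: "Per-protocol (PP) and intention-to-treat (ITT) analysis are performed where comparison is made within-group". The sentence goes on to include the between-group comparison, and the Project Summary says the same. The between-group test is an independent t-test on changes, two-sided at P<0.05, with no distinction between the two analysis sets. Missing data are to be multiply imputed. The section does not say which set is primary, which patients form the PP set, or what level of adherence would qualify.

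Three sections bear on who could be judged to have followed the protocol:

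- **Assessment of dietary plan adherence.** The rule is: "If the diary indicates that the participants eat an extra calorie on a fasting day, that day is labelled as" not adherent. The percentage has as its denominator "Number of fast days in week".
- **Sampling Frame, withdrawal criteria.** The first is "Subject who unable to tolerate alternate daily fasting intervention during the trial". The second is "Patient own choice".
- **Control group.** "All participants in the control group will continue their usual habitual diet for 8 weeks", and "No specific dietary advice or educations are provided throughout the entire trial". No adherence criterion is given for controls. Problems Anticipated describes the dietician sessions as "given to participants in interventional group to monitor the calorie intake".

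**The concern.** ITT compares the groups as randomised. A PP comparison does so only if the exclusions are unrelated to prognosis or act alike in both arms. Here the only stated ways of failing the diet exist in MACR. Patients who abandon or break a fasting regimen may be less motivated, and might have lost less weight and improved less on any regimen. Removing them from MACR, with no matching selection among controls, would raise the MACR average without any effect of the diet.

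This matters because PP stands beside ITT with equal status and the same significance rule, and the protocol itself lists dietary compliance as an anticipated problem. With PP undefined, its criteria could be settled after the data are seen. A favourable PP result beside a null ITT result could then be read as showing that the diet works when followed, which this contrast cannot show.

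**Working it through.** **Which criteria can a patient fail in each arm?**

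| Criterion (section) | MACR | Control |
|---|---|---|
| Fast-day adherence (Assessment of dietary plan adherence) | yes | no: no fast days, so the percentage has a zero denominator |
| Cannot tolerate fasting (Sampling Frame) | yes | no |
| Withdrawal by own choice (Sampling Frame) | yes | yes |
| Starts metformin or a thiazolidinedione (Management of diabetes medications) | yes | yes |
| Misses the post-intervention assessment (Procedures) | yes | yes |

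The first two rows are one-sided and the last three are not. The asymmetry therefore depends on which rows define PP, and the plan does not say.

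**How large could it be?** The plan gives no figure to reproduce on this point.

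*Inputs from the documents:* 46 participants, three MACR to one control, so 46 × 3/4 = 34.5 and 46 × 1/4 = 11.5, taken as 34 and 12; independent t-test; two-sided 0.05.

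*Assumptions not in the documents:* no true diet effect; outcome change standard normal (higher = better); correlation rho between adherence tendency and outcome change apart from the diet; the k least adherent MACR patients removed; no controls removed.

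*Formula.* With f = k/34 and z the f-quantile of the standard normal, the bias in SD units is approximately rho × φ(z)/(1 − f).

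- k = 5: f = 0.147, φ(z) = 0.230, multiplier 0.230/0.853 = 0.270
- k = 8: f = 0.235, φ(z) = 0.308, multiplier 0.308/0.765 = 0.403
- k = 12: f = 0.353, φ(z) = 0.372, multiplier 0.372/0.647 = 0.575

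For example, k = 8 and rho = 0.5 gives 0.5 × 0.403 = 0.20 SD. Simulating the planned t-test (40,000 trials per setting, Monte Carlo error 0.1-0.2 percentage points) gives:

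| MACR removed | rho | Bias (SD) | Two-sided type I error |
|---|---|---|---|
| 5 (about 15%) | 0.1 | 0.03 | 5.0% |
| | 0.3 | 0.08 | 6.0% |
| | 0.5 | 0.13 | 7.4% |
| 8 (about 25%) | 0.1 | 0.04 | 5.2% |
| | 0.3 | 0.12 | 6.5% |
| | 0.5 | 0.19 | 9.4% |
| 12 (about 35%) | 0.1 | 0.06 | 5.2% |
| | 0.3 | 0.17 | 7.8% |
| | 0.5 | 0.28 | 13.4% |

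At rho = 0 the bias is nil and the error is 5% in every case.

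For scale, the standard error of the contrast with 26 v 12 is √(1/26 + 1/12) = 0.35 SD. The bias at k = 8 and rho 0.3-0.5 is therefore about a third to just over half of one standard error. In those two settings, PP is significant in favour of MACR while ITT is not in about 3-6% of null trials.

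**Do control losses cancel it?** Only if they select on the same trait. With 8 MACR patients removed and rho 0.3-0.5, dropping 3 of 12 controls at random leaves the bias at 0.12-0.20 SD. Dropping the 3 controls lowest on the same tendency removes it. The plan has no rule that would do the second.

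**The case against.** A reader might infer that the planned PP analysis removes patients from MACR only. The documents do not support that. PP is never tied to the diary; adherence is measured for its own secondary objective; and PP could mean simply those who completed the final assessment. Controls too can leave by choice, start a barred drug or miss that assessment. That controls keep no diary after run-in is likewise inferred: no section says so, and the flow figure is not available. These limits stand, and the point is conditional for that reason. A control diary would still not yield a fast-day score.

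A reader might also infer that PP must favour MACR even if the diet does nothing. That needs both selection on adherence or tolerance and a positive correlation with outcome; at a correlation of 0.1 the error rate hardly moves. The calculation also assumes that the diary ranks patients perfectly. If the diary has reliability 0.5 (an assumption), removing 25% at correlations of 0.3-0.5 gives 0.08-0.14 SD and 5.5-7.1% two-sided error.

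Finally, ITT with multiple imputation is planned, so the randomised comparison will be available. This limits the harm but does not remove it, because the plan does not say that ITT decides the conclusion.

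**Conclusion.** The concern holds in conditional form. PP is undefined and has the same standing as ITT, and the plan's only diet-adherence measure and its intolerance criterion can apply only to MACR. A PP contrast built on them would be asymmetric, and the planned unadjusted t-test would not correct it. The direction favours MACR if adherence tendency predicts outcome apart from the diet. The size is modest to moderate over the assumed ranges: negligible at the low end, and at the high end enough to more than double the nominal error rate. These figures illustrate the risk; they do not predict this trial's bias.

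**What to change.** In Data management and statistical analysis:

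1. Name ITT, with the planned multiple imputation, as the analysis on which effectiveness is concluded.
2. Define PP before analysis, using only criteria that either arm can fail: for example, post-intervention assessment attended, no barred drug started, and no outside weight-loss programme or drug. The last is now only an entry exclusion, so it would have to be recorded during follow-up in both arms. Do not use fast-day adherence to select the set.
3. Report PP as supportive, with no significance claim, and give the number and reasons for exclusion by arm. Attendance can itself differ by arm through intolerance, so two-arm criteria reduce the problem but do not guarantee balance.

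A complier estimate (the ITT difference divided by the fraction p of MACR reaching a stated adherence level) is optional at most. If patients below that level gain Δn and those above gain Δc, the ratio estimates Δc + Δn(1 − p)/p, which overstates Δc when Δn is positive. That is plausible here: one day with extra calories is labelled non-adherent although the patient may still be fasting in part, and every MACR patient is offered dietician visits and calls.

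The cost is a few lines of text, a little recording in both arms, and one table of exclusions. The downside is that a PP result could no longer support a claim of effectiveness by itself.
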